Participants will be solicited by investigators and consented prior to participation. Once consented, participants will be scheduled for their testing session(s) per protocol procedures. If enrolled, participants will be randomized to the order of the different settings on the HVT 2.0 device in different test sessions. Each participant will present on 4 different days for testing. This is to avoid fatigue related changes in sequential tests. Additional testing sessions may be scheduled to complete data collection if needed.

Sample Size:

Because no data exist for variance around these parameters, we will plan to enroll 15 participants, each to perform 4 test sessions.

Data Safety Monitoring:

Given that this protocol is a conventional exercise test protocol and therefore very low risk and routinely performed without physician oversight, there is no plan for a Data Safety Monitoring Board. Any adverse events (AE) will be promptly reported to the IRB for consideration.

VI. Study Procedures

Screening, Enrollment, & Management

During screening, participants will be asked to participate in this study, and if so, they will provide informed consent prior to enrollment. Participants will be instructed that if at any time during the study that they wish to discontinue the study, they are free to stop the testing and discontinue study participation at any time. All study procedures will be explained to the participant prior to starting any procedures, and all participants will be given a copy of the informed consent form.

Participants will be scheduled for test sessions to complete the objectives of the study and instructed to wear exercise appropriate clothing. Participants will be informed that prior to each test session, they should abstain from caffeine or tobacco products for a minimum of 4-hours, and alcohol and strenuous exercise for 10-hours ¹⁰. Participants are instructed that if at any time during the study he/she feels faint, dizzy, short of breath, or for any reason, they should stop the test.

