	Study Start	After Warm-Up	Exercise Period q60sec	Recovery Period q5min	Study End
Participant pertinent Medical History	X				
Participant Vitals * (HR, RR, SpO₂, BP)	X	X	X	X	
Lactate [La]	X	X	X	X	
Dyspnea (Borg scale)	X	X	X	X	
Perception Scores (1-10 scale)					X
Work Performance			X		

*Vitals only measured prior to start of exercise, after exercise period ends, and after recovery interval. If practical, may record real-time the HR, RR, and SpO₂ with digital sensors. This will be completed for each Therapy Settings designated in the Study Protocol.

Data collection during enrollment will include participant demographics (e.g., age, gender, height, weight). Each Therapy Settings will collect the relevant participant vitals, lactate levels, dyspnea scores, and perception scores.

Primary Endpoint

- Change in lactate over (1) the exercise test interval, and (2) the recovery interval

Secondary Endpoints

- Participant Vitals: HR, RR, SpO₂, BP
- Dyspnea Score: modified BORG score, 1-10 scale
- Exercise Test Work Performance: peak power output, mean power output over 60 seconds, and decrease in power (fatigue index)

Tertiary Endpoint

Participant Perception of Performance/Recovery [1-10 scale]

- Level of Exertion at Exercise End: "How tired do you feel?"
- Relief of Exertion at Recovery End: "How fast do you feel you recovered?"

- Comfort/Tolerance of Therapy at Therapy Segment End: "How comfortable was the therapy while you had it on during exercise? How comfortable was the therapy while you had it on during recovery?"

VIII. Statistical Analysis

Participant demographics and characteristics will be summarized, compared, and appropriate statistical testing will be performed for the continuous and categorical variables. Descriptive analyses of the primary endpoints, supporting data/variables, and secondary outcome data will be performed. Assuming a non-normal data distribution for this study, a non-parametric test (e.g., Wilcoxon Signed Rank Sum test) will be performed with significance interval of 0.05 on all applicable variables. If continuous variables present a normal distribution, between-trial comparisons will be performed using two-way (within-within; trial* post-exercise sampling times) repeated measures ANOVAs. Otherwise, for the categorical variables, the Fisher's Exact test will be performed. Further analyses may be performed on the collected data based on ongoing analyses at time of study completion to identify additional relevant results.

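### An unspecified normality judgement, made after the data are seen, switches the primary analysis between two methods that test different questions

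*Combined protocol and SAP*

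**What the plan says.** Section VIII begins its inferential plan with "Assuming a non-normal data distribution for this study" and gives the Wilcoxon signed-rank test as an example of the non-parametric test to be used. The test "will be performed with significance interval of 0.05 on all applicable variables". The next sentence introduces the alternative: "If continuous variables present a normal distribution, between-trial comparisons will be performed using two-way" repeated measures ANOVA, in which both factors are within-participant: setting (called trial) and post-exercise sampling time.

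The section does not say:
- how normality is judged, or on what scale (levels, changes, paired differences or residuals);
- whether the judgement is made per setting and time, pooled, or variable by variable;
- which lactate summary and which pair of settings the signed-rank test would use;
- which ANOVA term would be primary.

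It ends by allowing further analyses guided by the data. On size, Section V says "Because no data exist for variance around these parameters", "we will plan to enroll 15 participants, each to perform 4 test sessions".

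Section II defines the primary endpoint as one lactate change, from before exercise to recovery. Section VII defines two changes, over exercise and over recovery. The secondary endpoints in Section VII include peak power, mean power and fatigue index, all measured during the exercise test.

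**The concern.** The choice between the two branches depends on how the collected data look, so the primary test is not known until then. Four things follow.

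1. **The question changes.** A signed-rank test compares two settings on one number per participant. The ANOVA tests four settings, and the interaction of setting with time, over the post-exercise samples.
2. **The check may look at the wrong quantity.** On the plain reading it concerns the variables themselves. In a within-participant design, the distribution that matters is that of the paired differences or residuals.
3. **Mixed results are not covered.** Lactate is measured in many setting-by-time cells, and some may look normal while others do not.
4. **The ANOVA branch does not fit some endpoints.** Peak power, mean power and fatigue index have no post-exercise sampling times.

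At stake is whether the reported p-value belongs to a test that was fixed in advance. The background section says that the data may found a larger study, which makes this matter more than the trial's size suggests.

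**Working it through.** There is no planned power or effect size to reproduce: 15 participants is stated without a calculation.

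**Inputs from the protocol.** 15 participants, 4 settings, alpha 0.05. Recovery samples: Section VI asks for at least 15, while Table 1 has one every 5 minutes over a recovery of up to 1 hour.

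**Assumptions not in the protocol.** Shapiro-Wilk at 0.05; lognormal skew; the correlations given below.

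**Number of lactate cells.** 15 x 4 = 60 from Section VI. From Table 1, 60/5 = 12 times, and 12 x 4 = 48.

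**Step 1: how well the check detects skew at n = 15.** The skewness of a lognormal with log-scale SD s is (exp(s²) + 2) x sqrt(exp(s²) - 1).

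| s | Skewness | Flagged |
|---|---|---|
| 0.3 | 0.95 | about 19% |
| 0.5 | 1.75 | about 39% |
| 0.7-0.75 | 2.9-3.3 | about 61-65% |
| 1.0 | 6.2 | about 82% |

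Normal data are flagged in 4.8%.

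**Step 2: variables against paired differences.** Participant levels are lognormal, within-person noise is normal, and the noise SD is half the between-participant SD. The differences are then exactly normal.

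| Count | Values at a setting | Paired differences |
|---|---|---|
| One | about 12-39% | about 5% |
| Any (4 settings; 6 differences) | about 30-61% | about 26% |

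Each row compares like with like. An any-of-four count must not be set against a single difference.

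**Step 3: mixed results when everything is normal.** At least one lactate cell is flagged in about 79-96% of trials with 60 cells, AR(1) correlation over time of 0.7-0.9 and participant correlation of 0.3-0.6. Wider assumptions, including participant correlation of 0.8, give about 54-96%.

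**Step 4: the two branches on the same data.** Simulated trials had 15 participants, 4 settings and 12 times, with AR(1) 0.8 and within-session SD 1. The signed-rank tests used the change from first to last recovery sample, for all 4 x 3/2 = 6 pairs of settings.

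| Scenario | Any of 6 signed-rank | ANOVA setting | ANOVA interaction, uncorrected |
|---|---|---|---|
| No effect | 21% | 5% | 13% |
| Level shift of 0.8 in both high-flow settings | 21% | 96% | 15% |
| Slopes diverging to 1.2 in both high-flow settings | 91% | 77% | 83% |

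A constant shift cancels in a first-to-last change, so the second row is a consequence of that choice of summary. A change from the pre-exercise value would not cancel it. The protocol does not say which summary applies, so the branch taken can decide the conclusion. For comparison, six independent tests at 0.05 would give 1 - 0.95^6 = 26.5%.

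**Step 5: type I error of switching.** In a simplified version, the check chose between a paired t test and a signed-rank test for one contrast. Type I error was 4.7-4.9%. Taking the smaller of the two p-values gave 5.3-5.9%.

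**Step 6: endpoints without sampling times.** Section VI computes the three power indices during the 60-second test. Section II describes mean power over 30-second intervals. On either wording the values arise during exercise, so a factor for post-exercise time does not exist for them. If they look normal, the plan directs an analysis that cannot be run.

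**The case against.** The strongest defence is that this is a feasibility study with a declared non-parametric default, and that switching to a parametric test when the data allow it is common practice. The pilot status and the default do soften the impact. They do not remove the defect, because the alternative here is a different analysis of a different set of data, not a parametric version of the same test.

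Four stronger readings are tempting, and the documents do not support them.

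- **That the check is certainly made on raw values.** This is the plain reading of the sentence, but no scale is named. The primary variable is itself a change in lactate. The signed-rank test is also only an example, and the text does not say that it uses one value per person.
- **That the check is close to arbitrary at n = 15.** That fits mild to moderate skew only. Marked skew is detected in 61% or more of samples. If 60 independent values were pooled, detection at s = 0.4-0.5 would be 87-97%, although four sessions from each of 15 participants are not independent.
- **That the switch inflates the type I error.** Step 5 shows no inflation in the simplified case, and the full rule is too loosely stated to test. The 21% and 13% in the no-effect row of Step 4 reflect multiple pairs and an uncorrected interaction test, which are separate matters.
- **That unblinded analysts will pick the branch they prefer.** Section IV calls the trial unblinded and says nothing about who analyses it or what they know.

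**Conclusion.** The concern holds in a limited form. The protocol states a rule that moves the primary analysis from one question to another on an undefined, data-dependent judgement. The rule has no provision for mixed results over about 48-60 lactate cells, and it cannot be carried out for three named secondary endpoints. These conclusions come from the text and need no simulation.

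The size of the unreliability is conditional on Shapiro-Wilk at 0.05, lognormal skew and the assumed correlations. Under them, the check misses mild to moderate skew in about 61-81% of samples (100% minus 39% and 19%). It also flags variables whose paired differences are exactly normal, in about 12-39% of trials for one setting. The harm is a changed estimand and a primary test not fixed in advance. The sponsor should correct this. With a pilot design and a stated default, it does not by itself invalidate the study.

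**What to change.** Delete the normality switch from Section VIII and replace it with the following.

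1. Name one lactate summary that reflects recovery or clearance, computed per session from the recovery samples, and make Sections II and VII agree on it.
2. Name one primary contrast. High flow (settings 2 and 3) against low flow (settings 1 and 4) suits the hypothesis, which is stated to hold regardless of FiO₂.
3. Analyse that summary, and each continuous endpoint with a single value per session, with one within-participant model: setting and period as fixed effects, participant as random. Period belongs in the model because the order of settings is randomised over four days.
4. Decide now whether lactate is log-transformed.
5. Give a signed-rank or within-participant permutation test of the same contrast as a sensitivity analysis.
6. Report residual checks, but do not use them to choose the analysis.

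The setting-by-time analysis of the lactate curve can stay as a secondary analysis, so the recovery profile is not lost. The cost is SAP wording and one sensitivity analysis, with no change to recruitment, sessions or sampling. The model relies on roughly normal residuals with only 15 participants, which is what the sensitivity analysis is there to cover.

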The **hypothesis** is that HVT, regardless of the oxygen concentration (i.e., FiO₂), will reduce the work of breathing and increase the lactate clearance rate during exercise and recovery intervals.

To test this hypothesis, the study will be conducted with the following specific aims:

Aim #1: Primary Outcome.

The primary endpoint is change in blood lactate from before the exercise test to recovery over a period of 30-60 minutes post-exercise.

Aim #2: Secondary Outcomes.

The secondary endpoints evaluate additional data that may be clinically meaningful. Data will include vital signs (SpO₂, heart rate [HR], respiratory rate [RR], blood pressure [BP]), and perceived level of exertion (BORG [score 0-10]), as measured during the exercise and recovery intervals. Work performance will be computed during test period only, including peak power output, mean power output over 30second intervals, and decrease in power.

Aim #3: Tertiary Outcomes.

The tertiary endpoints will evaluate the participant perceptions of the therapy impact during study procedures: (1) Level of Exertion at Exercise End, (2) Relief of Exertion Recovery End, (3) Comfort/Tolerance of Therapy at Study End [exercise and recovery], as measured on a 1-10 Likert scale.

1. Level of Exertion at Exercise End: "How tired do you feel?"
2. Relief of Exertion at Recovery End: "How fast do you feel you recovered?"
3. Comfort/Tolerance of Therapy at Therapy Segment End: "How comfortable was the therapy while you had it on during exercise? How comfortable was the therapy while you had it on during recovery?"

These **endpoints** will establish the effect of Vapotherm HVNI on lactate clearance, work of breathing, and perceived exertion during exercise and recovery intervals.

III. Participant Selection

Participants will be identified and recruited by study investigators. The study will take place in an appropriate educational forum (e.g., hospital, academic center, laboratory setting, etc.) where kinesiology testing can be accomplished. Initial contact will be made by study investigators, and volunteers may include any interested participants. Participants will be compensated for their time at a rate of approximately **\$50 per hour**.

Inclusion Criteria

1. Adults over 18 years old, in a general state of good health, of either sex
2. No known contraindication to performing a maximal exercise test, i.e., Wingate-type Anaerobic exercise test

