Data collection during enrollment will include participant demographics (e.g., age, sex, height, weight). At each session, participant vital signs, lactate levels, dyspnea scores, work performance indices, and perception scores will be collected. The study will include four sessions, corresponding to four therapy settings being tested: (1) FiO₂=100% with Flow=5LPM, (2) FiO₂=21% with Flow=25-30LPM, (3) FiO₂=100% with Flow=25-30LPM, (4) FiO₂=21% with Flow=5LPM.

For each **test session** of the four HVT Settings, the following procedures will be followed.

Pre-Test Preparations:

Prior to starting the test, the participant will perform 2-3 second warm up sprints to acclimate to the ergometer. The cycle ergometer seating settings will be maintained consistent across all four therapy settings. Participants will be instrumented appropriately and initial data (e.g., vital signs, lactate, dyspnea) will be collected for baseline.

Wingate-type Exercise Test Procedures:

The exercise test model is called the Wingate anaerobic test. In a pre-test, the participants will Wingate test consists of pedaling with maximal effort for a series of short 8-second intervals against different loads, separated by 5 min of rest. This pre-testing is done to determine the load required for maximal power output. For the actual Wingate-type test, the participant will pedal as rapidly as possible for 60 sec against the load determined for maximal power output. Three indices of performance will be computed during the test period – peak power output, mean power output over the 60 seconds, and decrease in power (fatigue index).

At end of exercise interval, participant will be asked their perception of their level of exertion.

Recovery Interval:

Recovery interval will take place after exercise period up to 1 hour, or until participant is fully recovered and lactate levels approach baseline. A minimum of 15 samples during the recovery interval will be performed to complete lactate recovery data evaluation.

At end of recovery interval, participant perception of (1) Relief of Exertion at Recovery End, and (2) Comfort/Tolerance of Therapy will be recorded.

Sessions will be repeated on separate days, scheduled at the convenience of participant and laboratory, until a participant has completed a session at each of the HVT setting levels.

VII. Data Collection

Table 1. Key study data and collection points for each Phase of the Study.

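### The conditional repeated-measures ANOVA needs a full setting-by-time grid, but recovery sampling may stop once lactate nears baseline, and no rule covers the empty late cells.

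*Combined protocol and SAP*

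**What the plan says.** Section VIII sets a default and a conditional branch. The default is "a non-parametric test (e.g., Wilcoxon Signed Rank Sum test) will be performed with significance interval of 0.05 on all applicable variables". If continuous variables look normal, the settings are instead compared by "two-way (within-within; trial* post-exercise sampling times) repeated measures ANOVAs". The sampling times that form the time factor are not listed.

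The length of recovery is not fixed. Section VI (Recovery Interval) says: "Recovery interval will take place after exercise period up to 1 hour, or until participant is fully recovered and lactate levels approach baseline". No numerical value defines nearness to baseline. Aim #1 in Section II runs the primary endpoint from before exercise "to recovery over a period of 30-60 minutes post-exercise", so unequal lengths are intended.

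Section VI also asks for a minimum number of samples: "A minimum of 15 samples during the recovery interval will be performed to complete lactate recovery data evaluation". Table 1 in Section VII puts recovery sampling at 5-minute intervals.

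On size, Section V says: "Because no data exist for variance around these parameters, we will plan to enroll 15 participants, each to perform 4 test sessions". The documents contain no rule for missing time points.

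**The concern.** A within-within ANOVA in its classical form works on a rectangle: each participant supplies one value for each setting at each time. The protocol lets that rectangle have gaps at the late times. These gaps are not deviations, since a session that ends on recovery has followed the protocol. They are also not random. A session ends early because lactate has cleared, and faster clearance at high flow is what Section II hypothesises.

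The analyst would then have to delete participants with any gap, cut the grid to the shortest session, fill the gaps or change the method. The plan chooses none of these, so the choice would be made after the data are seen. Deletion would remove participants with at least one fast-clearing session, from only 15 enrolled. This is more than a missing detail, because the named analysis and the stated end of sampling do not fit together.

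**Working it through.** The plan's figure of 15 participants cannot be reproduced, because no effect size, standard deviation or power is given. The checks below use stated design figures where they exist and labelled assumptions elsewhere.

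**1. Schedule.** Inputs: 5-minute interval (Table 1), 1-hour limit and 15-sample minimum (Section VI).
- 60 / 5 = 12 samples in an hour, or 13 with one at time zero.
- 15 samples at 5-minute spacing end at 14 x 5 = 70 minutes (first at zero) or 15 x 5 = 75 minutes (first at 5 minutes).
- 15 samples in 60 minutes need one every 60 / 15 = 4 minutes; in 30 minutes, one every 30 / 15 = 2 minutes.

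The three statements cannot all hold. With 12 to 15 times, the ANOVA needs 4 x 12 = 48 to 4 x 15 = 60 filled cells per participant.

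**2. Complete participants under listwise deletion.** Let p be the chance that a session ends early (assumed). Independent sessions give 15 x (1 - p)^4; fully dependent sessions give 15 x (1 - p).

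| p | Independent | Fully dependent |
|---|---|---|
| 10% | 15 x 0.9^4 = 9.8 | 15 x 0.9 = 13.5 |
| 25% | 15 x 0.75^4 = 4.7 | 15 x 0.75 = 11.3 |

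The truth should lie between the columns, because a participant who clears fast tends to do so in every session.

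**3. Precision.** The paired difference detectable with 80% power at two-sided 0.05 (normal approximation; the plan does not state sidedness) is (1.96 + 0.84) / sqrt(n): 0.72 SD at n = 15, 0.89 at n = 10 and 1.14 at n = 6.

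**4. Illustrative simulation.** All inputs are assumed: exponential clearance at 0.04 per minute, baseline 1.2 and peak rise 12 mmol/L, sampling every 5 minutes to 60 minutes but stopped at 2.0 mmol/L, clearance 15% faster at high flow, log-rate SD 0.25 between participants and 0.1 between sessions.
- Median time to threshold is ln(12 / 0.8) / 0.04 = 67.7 minutes at low flow and 67.7 / 1.15 = 58.9 minutes at high flow.
- About 40% of high-flow and 22% of low-flow sessions end early, 31% overall.
- On average 7.6 of 15 participants are complete. Independence would predict 15 x 0.69^4 = 3.4, so dependence between sessions matters.
- The standard error is about 1.5 times that with all 15.
- The clearance-rate effect among complete cases falls from 15.0% to about 13.7%.
- On mean lactate, the scale the ANOVA uses, the ratio of complete-case to full-data effect is about 0.98. It is 1.04 with session SD 0.05 and 0.85 with 0.2.

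**5. Wider range.** Assumed half-lives of 12 to 22 minutes, thresholds of 1.7 to 2.5 mmol/L, clearance 20% faster at high flow, log-SD 0.1 to 0.4 between participants and 0.05 to 0.2 within.
- With a common proportional effect, the lactate-scale ratio runs from 0.78 to 1.16.
- If the effect is larger in fast clearers, the ratio is 0.66 or below and can change sign; if larger in slow clearers, it is 1.23 to 1.51.
- With no true effect there is no bias, only loss of participants.
- If every session is sampled to 60 minutes, all 15 remain and the ratio is 1.00.

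**The case against.** The strongest reply is that the ANOVA is only the conditional branch. If the default non-parametric test is applied to one lactate change per session, no grid is needed and an early-ended session still counts. That is correct and limits the point. But the ANOVA is prespecified for continuous variables that look normal, lactate may qualify, and it is the only named method that uses the recovery time course.

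Second, the plan never says that incomplete participants are deleted. A reader might infer that it does; that is the method's usual handling, not the plan's text. A 0-30 minute grid would also be compatible with Aim #1 and would delete nobody if every session reached 30 minutes. This stands as a way out, but the plan does not take it.

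Third, 15 samples at 5-minute spacing would rule out early stopping. That works only by overrunning the hour. If the minimum is met by closer sampling, early stopping is possible again and times may differ between sessions.

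Fourth, Section V allows extra sessions to complete data collection, and Section XII treats missed readings as deviations. Neither is tied to sessions that ended on recovery, which are complete under Section VI.

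Finally, a reader might infer that losing the fast clearers must pull the flow effect toward no difference. The documents do not support this: they give no lactate kinetics or variance, and under plausible assumptions the lactate-scale effect moves either way.

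**Conclusion.** The conflict holds, within limits. The conditional ANOVA needs a complete grid, the protocol permits outcome-dependent gaps, and no rule connects the two. Under complete-case handling the loss could be modest (13.5 of 15 remaining) or severe (4.7 of 15), depending on how often sessions end early and how strongly sessions within a participant agree. For a study of 15 with no power calculation, that is a material loss of precision.

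Bias is possible, but neither its direction nor its size can be stated. The retention counts rest on assumed early-stopping rates and on listwise deletion; the simulation results rest on assumed kinetics. Confidence is high in the structural mismatch and low in any particular figure for bias. As this is a pilot meant to inform a larger study, the change is advisable rather than critical.

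**What to change.** Replace the complete-grid ANOVA in Section VIII with one of these, chosen before the data are seen:

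1. A linear mixed model on all observed lactate samples, with setting, time and their interaction as fixed effects and participant random effects. A further random effect for session within participant would allow for correlation among samples in one session. If stopping follows the recorded lactate values, the gaps depend on observed data, which a likelihood-based model can accommodate when its time course and covariance are adequately specified.
2. A per-session clearance summary over a window that every session completes, for example end of exercise to 30 minutes. This can also feed the default paired non-parametric test. The plan should confirm that every session reaches the end of the window, because Section VI itself states no minimum duration.

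Under either option, list the lactate sampling times and state that early-ended sessions stay in the analysis. Separately, the sponsor must reconcile the 15-sample minimum, the 5-minute interval and the 1-hour limit in Sections VI and VII.

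The analysis change costs SAP wording and routine software, with no extra data. If the common window is chosen, later samples carry less weight in the main comparison.

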3. **Participants must consider themselves able to perform "regular moderate" or "regular strenuous" exercise.**

- a. "Regular moderate" exercise includes less than 30 minutes every day or 30 minutes every other day, of some form of deliberate exercise, that does not include walking.⁷
- b. "Regular strenuous" exercise is 30+ minutes per day, of some form of deliberate exercise, that does not include walking.⁷

Exclusion Criteria

1. Not considered a 'high-performance athlete'
2. Known active cardiovascular, metabolic, liver, or renal disease^{8,9}
3. Orthopedic limitations to exercise¹⁰
4. Pregnancy¹⁰
5. Use of beta-blockers or beta-agonist asthma medications¹⁰
7. Exercise induced asthma
8. Any other health-related issue that would involve the participant's fitness capability
9. Inability to complete all of the study procedures

IV. Study Design

The feasibility/pilot study will be performed as a prospective, unblinded clinical trial of a Wingate-type Anaerobic exercise test. Submaximal cycle ergometry tests are routinely used in exercise, kinesiology, and rehabilitation facilities, typically without physician supervision, to assess fitness level and/or physiologic response to exercise and pose minimal risk. The study will take place in an exercise kinesiology and rehabilitation laboratory facility setting.

The study is a repeated measures model that will collect data on the participants with the designated HVT at four specified settings (Flow/FiO₂) during the Wingate exercise test and during the recovery interval. The Wingate exercise test configuration, equipment and procedures will be repeated for each HVT setting for a matched dataset. Participants who fit criteria will be asked to consent to enroll in the study.

The study will include four study arms, corresponding to four therapy settings being tested: (1) FiO₂=100% with Flow=5LPM, (2) FiO₂=21% with Flow=25-30LPM, (3) FiO₂=100% with Flow=25-30LPM, (4) FiO₂=21% with Flow=5LPM. The participants will wear the appropriately sized nasal cannula interface during the exercise and recovery.

V. Participant Enrollment

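### Fisher's exact test is named for categorical variables in a matched crossover, so any categorical comparison between settings would ignore the pairing (minor)

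*Combined protocol and SAP*

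**What the plan says.** Section IV (Study Design) describes a within-person design: "The study is a repeated measures model that will collect data on the participants with the designated HVT at four specified settings". The test configuration "will be repeated for each HVT setting for a matched dataset". Section V (Participant Enrollment) adds that "participants will be randomized to the order of the different settings", and sets the size: "Because no data exist for variance around these parameters, we will plan to enroll 15 participants, each to perform 4 test sessions". There are no parallel groups.

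Section VIII (Statistical Analysis) names three methods:
- a non-parametric test, with the "Wilcoxon Signed Rank Sum test" as the example, at the 0.05 level on all applicable variables;
- a within-within repeated measures ANOVA, if continuous variables are normal;
- for the rest: "Otherwise, for the categorical variables, the Fisher's Exact test will be performed".

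No paired test for categorical data is named. The section does not list the categorical variables, and it does not say what Fisher's test would compare. Section VII lists the endpoints: lactate, vital signs, a Borg dyspnea score, power indices, and "Participant Perception of Performance/Recovery [1-10 scale".

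**The concern.** Fisher's exact test compares proportions in independent samples. Here every setting contains the same people, so two settings give 15 pairs, not 30 independent observations. If responses within a person are positively correlated, the difference between settings varies less than the test supposes. Its p-values are then too large.

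The section is also inconsistent with itself, because the signed-rank test and the repeated measures ANOVA both respect the pairing and only the categorical branch drops it. With 15 participants, the within-person comparison is the main source of precision. An analyst who followed the sentence literally for a between-setting comparison would discard it.

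**Working it through.** **What can be reproduced.** Nothing numerical. The plan gives no power, effect size, response rate or within-person correlation, and 15 is a planning choice. The documents supply n = 15, four settings and the 0.05 level. Sidedness is not stated, so two-sided is assumed. All rates, score means, SDs and correlations below are assumptions.

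**Two settings, binary outcome (exact enumeration).** Let p1 and p2 be the two rates and ρ the latent normal correlation. Then

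- p11 = Φ₂(Φ⁻¹(p1), Φ⁻¹(p2); ρ), p10 = p1 − p11, p01 = p2 − p11, p00 = 1 − p11 − p10 − p01;
- power is the sum of multinomial(15; p11, p10, p01, p00) probabilities over all tables with p ≤ 0.05;
- Fisher uses only the two totals, and exact McNemar uses only the discordant pairs, tested as binomial(½).

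For 30% versus 70% at ρ = 0.5: p11 = 0.267, p10 = 0.033, p01 = 0.433, p00 = 0.267.

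| Rates | ρ | Fisher | Exact McNemar |
|---|---|---|---|
| 30% vs 70% | −0.3 | 44% | 38% |
| 30% vs 70% | 0 | 43% | 43% |
| 30% vs 70% | 0.5 | 41.6% | 52.3% |
| 30% vs 70% | 0.7 | 40.7% | 56.6% |
| 30% vs 70% | 0.8 | 40.2% | 58.4% |
| 10% vs 50% | 0 | 54% | 49% |
| 10% vs 30% | 0.5 | 11.2% | 8.1% |
| 10% vs 30% | 0.8 | 8.5% | 6.7% |
| 5% vs 20% | 0.5 | 6.1% | 2.5% |
| 50% vs 50% (null) | 0.5 | 0.37% | 0.89% |
| 50% vs 50% (null) | 0.8 | 0.04% | 0.18% |

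The reversal for uncommon events has a simple cause. Exact McNemar needs at least six discordant pairs: 2 × 0.5⁶ = 0.031, but 2 × 0.5⁵ = 0.063. At 10% versus 30% and ρ = 0.5 the expected number is 15 × (0.035 + 0.235) ≈ 4.

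**A single data set.** Take 15 pairs: 3 yes/yes, 6 discordant one way, 0 the other way, 6 no/no. The totals are 9/15 and 3/15. Fisher gives p = 0.060 and exact McNemar gives p = 2 × 0.5⁶ = 0.031.

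**Four settings, binary outcome (4,000 simulated trials per case).** Fisher-Freeman-Halton on the 4 × 2 table is compared with Cochran's Q = 3(4ΣCⱼ² − T²)/(4T − ΣRᵢ²), where Cⱼ are setting totals, Rᵢ participant totals and T the grand total. Q is referred to χ² with 3 degrees of freedom.

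| Rates | ρ | Fisher | Cochran's Q |
|---|---|---|---|
| all 0.5 (null) | 0 | 4.8% | 5.1% |
| all 0.5 (null) | 0.5 | 1.0% | 4.8% |
| all 0.5 (null) | 0.7 | 0.2% | 4.4% |
| 0.3/0.5/0.5/0.7 | 0 | 41% | 41% |
| 0.3/0.5/0.5/0.7 | 0.5 | 34% | 56% |
| 0.3/0.5/0.5/0.7 | 0.7 | 29% | 66% |

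These rows show the cost of ignoring the pairing most cleanly, because discreteness matters little here: both tests are near 5% at ρ = 0.

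**A 1-10 score, two settings (3,000 simulated trials per case).** Assume means 5 and 6 and SD 1.5. At ρ = 0.5, Wilcoxon signed-rank has 62% power, against 13% for Fisher on the score cut at 6 or more. At ρ = 0 the figures are 36% and 17%, so a good part of that gap comes from cutting the score rather than from lost pairing.

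**The case against.** The strongest reply is that the sentence may never be applied to a comparison between settings. No listed endpoint is binary or nominal. Sex is the one clearly categorical item named, and it cannot differ between settings when the same people are in each. Section VIII opens with demographics, so the Fisher sentence may refer to those. Adverse events are to be reported and early stops are allowed for, but neither is planned as a comparison. This stands, and it is why the point is minor. It does not make the sentence right: with no parallel groups, the plan shows no evident use for Fisher's test.

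Two stronger readings are tempting, and the documents support neither.
- A reader might infer that the Borg and 1-10 scores are assigned to Fisher's test. They can equally be read as covered by the paired signed-rank test on all applicable variables. The plan is ambiguous here, not clearly wrong.
- A reader might infer that Fisher's test always loses power in this design. That needs positive within-person correlation, which is plausible but not given, and outcomes that are not rare. At 10% versus 30%, Fisher has more power than exact McNemar even at ρ = 0.8.

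It is also fair to say that Fisher's very low null rejection rate with two settings is partly small-sample discreteness, since exact McNemar is far below 5% there too. With positive correlation the error is towards caution, so it would not create a false positive.

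**Conclusion.** The concern holds in a limited form. Fisher's independence assumption fails for any categorical comparison between settings, and the plan names no paired alternative. With positive correlation the test is over-conservative. Power can fall by about 11 to 18 points in the two-setting case (30% versus 70%, ρ 0.5 to 0.8), and by about 23 to 37 points in the four-setting case (0.3/0.5/0.5/0.7, ρ 0.5 to 0.7). These sizes rest on assumed rates and correlations, and the loss disappears without correlation or with uncommon events.

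The primary lactate endpoint is not affected. The practical reach is scores treated as categories, or any yes/no outcome that is compared by setting. In a 15-person pilot this is a minor point to consider. The hybrid name "Wilcoxon Signed Rank Sum test", which mixes the signed-rank and rank-sum tests, is editorial.

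**What to change.** Replace the Fisher sentence in Section VIII so that it:
- lists any categorical variables to be compared between settings;
- uses exact McNemar for binary outcomes at two settings, and Cochran's Q for four, in an exact or permutation version given n = 15;
- states that the Borg and 1-10 scores are analysed by paired rank methods, Friedman across the four settings and then Wilcoxon signed-rank;
- writes Wilcoxon signed-rank test as the name.

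The cost is a few lines of wording, with no extra data, visits or staff time. Doing it before analysis also removes a choice of test made after the data are seen.
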